#### **4.17.2 Safety Monitoring**

The study subjects will undergo frequent clinical evaluations including depressive scores, concomitant medications, adverse events, and serious adverse events and unexpected device events will be recorded from study entry through completion. Additionally, doctors must monitor a subject's safety by asking the subjects frequently about the subject's own comfort during treatment application.

If skin erythema is present, treatment will be suspended. Patients will be instructed to contact the study site principal investigator or a member of his staff at any time between visits concerning adverse events or worsening of symptoms. If at any study visit the subjects' clinical condition is significantly worsened from baseline (operationalized as the clinical global impression severity score, CGI-S, of 6 or higher) or if a subject becomes actively suicidal with intent and/or plan, based on the C-SSRS scale and/or the clinical interview, the subject will be offered to start an antidepressant medication. If the subject were deemed at imminent danger as a result of suicidality, s/he would be discontinued from the study and referred to appropriate clinical treatment (see 4.8.4 Termination).

The two site Principal Investigators (Drs. [name] and [name]) will have bi-weekly conference calls (which will include study RAs); during these conference calls they will discuss all Adverse Event reports to identify any safety concern, based on such concerns they will be able to decide temporary discontinuation of study enrollment, modifications of the study protocol, or to terminate the study.

Additionally, A Data and Safety Monitoring Board (DSMB), consisting of at least 2 clinicians and one biostatistician not directly involved in the study, will review SAEs annually. Research assistants responsible for data collection and storage will be aware of and comply with all regulatory requirements related to adverse events. In the event that a patient becomes ill or is injured as a direct result of study participation, medical care will be made available. All adverse events (and device events) will be followed to resolution and reported to the MGH IRB as serious in the event that **1.** they are unanticipated and possibly related to the study (same reporting as SAE) or **2.** if they meet any one of the following criteria: Any fatal event, immediately life-threatening event, permanently or substantially disabling event, event requiring or prolonging inpatient hospitalization, or any congenital anomaly. This also includes any event that a study investigator judges to impose a significant hazard, contraindication, side effect, or precaution.

Expedited review will occur for all events meeting the FDA definition of Serious Adverse Events (SAEs) – i.e., any fatal event, immediately life-threatening event, permanently or substantially disabling event, event requiring or prolonging inpatient hospitalization, or any congenital anomaly. This also includes any event that a study investigator or the DSMB judges to impose a significant hazard, contraindication, side effect, or precaution. For purposes of this study, all SAEs will be required to be reported to the DSMB, regardless of any judgment of their relatedness to the study device. All relevant information will be reported to the DSMB for each SAE including information about the event and its outcome, dosing history of all study TLT applications, concomitant medications, the subject's medical history and current conditions, and all relevant laboratory data. Per Partners IRB protocol, the principal investigator at each site will report all serious unanticipated adverse events to Insight/eIRB within 5 working days/7 calendar days of the date the investigator first becomes aware of the problem. If at any time during the course of the study, the DSMB judges that the risk to subjects outweighs the potential benefits, the DSMB shall have the discretion and responsibility to recommend that the study be terminated.

#### **4.17.3 Reporting Procedures for All Adverse Events**

After review with the subject by the study site personnel, all Adverse Events occurring during the study, whether or not attributed to the TPBM-1000 device or TLT procedure, observed by the Investigator or reported by the subject, will be documented in the subject's source document and on the appropriate CRF pages. The following attributes must be assigned:

1. Description of event
2. Date of onset
3. Date of resolution (if applicable)
4. Seriousness
5. Relationship to the study device and/or procedure(s)
6. Intensity

7. Action(s) taken
8. Outcome(s)

Intensity is defined as a measure of the severity of a reaction, effect or experience. The measurement(s) are described as mild, moderate or severe. The event itself, however, may be of relative minor medical significance.

The intensity of Adverse Events is assessed as mild, moderate or severe according to the following index scale:

**Mild**

The Adverse Event is transient, requires no treatment, and does not interfere with the subject's daily activity.

**Moderate**

The Adverse Event introduces a low level of inconvenience or concern to the subject and may interfere with daily activities, but is usually ameliorated by simple therapeutic measures.

**Severe**

The Adverse Event interrupts the subject's usual daily activity and requires systematic therapy or other treatment.

If the Adverse Event is of such intensity in the Investigator's judgment that it warrants withdrawal from the study, the subject should be withdrawn from treatment. The subject should be given appropriate care under medical supervision until symptoms resolve.

The relationship of an Adverse Event to the study device or procedure will be graded as follows:

**None**

The Adverse Event is not associated with the study device use.

**Remote**

The temporal association is such that the study device is not likely to have had an association with the observed Adverse Event.

**Possible**

This causal relationship is assigned when the Adverse Event:

- a) Follows a reasonable temporal sequence from device use, but
- b) Could have been produced by the subject's clinical state or other modes of therapy administered to the subject.

**Probable**

This causal relationship is assigned when the Adverse Event:

- a) Follows a reasonable temporal sequence from device use;
- b) Abates upon discontinuation of the treatment;
- c) Cannot be reasonably explained by known characteristics of the subject's clinical state.

**Definite**

This causal relationship is assigned when the Adverse Event:

- a) Follows a reasonable temporal sequence from device use;
- b) Abates upon discontinuation of the treatment; and
- c) Is confirmed by the reappearance of the Adverse Event on repeat exposure.

\*For purposes of immediate reporting of Unanticipated Adverse Events, investigator’s judgment will be considered for determining that the adverse event is “more than 50% likely” related to use of the device or to the treatment procedure.

#### **4.17.4 Serious Adverse Events**

All Serious Adverse Events must be reported to the overseeing Institutional Review Board (IRB), FDA, and Litecure Inc as required.

If the Investigators are notified by Litecure Inc or its designee of any Serious Adverse Events that are considered to be Unanticipated Adverse Device Effects, the Investigators must notify his/her own IRB/EC as required.

#### **4.17.5 Deaths**

Deaths which must be reported to Litecure Inc include all deaths while participating in the study.

#### **4.17.6 Withdrawals for Adverse Events**

All Adverse Events which result in the subject’s withdrawal from the study must be reported immediately by telephone to Litecure Inc.

The Investigator may be asked to provide detailed follow-up information. The Investigator will determine the reportability of the event on a case-by-case basis, and will report to the appropriate regulatory authorities evaluating the study device as necessary.

### ***4.18 Measures to Assure Subject’s Safety***

The Investigator will be responsible for monitoring the safety of subjects who enter this study and for alerting Litecure Inc of any study-related event that seems unusual and/or unanticipated for his/her site.

The Investigator will be responsible for the appropriate medical care of the subjects during the study in connection with protocol procedures for his/her site.

The Investigator will remain responsible for providing any appropriate health care options after a subject’s completion or discontinuation from the study due to adverse events.

## ***4.19 Subject Disposition Criteria***

### **4.19.1 Withdrawal from the Study**

Each subject and the Investigator reserve the right at any time to terminate a subject's participation in the clinical investigation.

Possible reasons for withdrawal or removal from the study may include:

1. The subject voluntarily withdraws consent.
2. The subject was not eligible based on the study inclusion and exclusion criteria.
3. The subject develops an Adverse Event that would not allow continuation in the study.
4. The subject has an Adverse Event which in the opinion of the Investigator warrants withdrawal from the study. Litecure Inc must be notified within two business days.
5. A decision is made by the subject and/or Investigator that the subject should be withdrawn from the study.
6. Subject death
7. Positive pregnancy test during the eligibility procedures

When a subject withdraws or is removed from the study, the following will be performed, if feasible, at the study termination (exit) visit:

- HAM-D-17
- QIDS-C
- CGI
- C-SSRS
- ADVERSE EVENTS FORM
- Concomitant medications form
- ASQ (self-rated)
- SAFTEE-SI (self-rated)
- SDQ (self-rated)
- NEURO-QOL (self-rated)
- SFI (self-rated),
- Cognitive tests

For all subjects who withdraw from the study prematurely, the date, and reason for withdrawal will be documented.

### **4.19.2 Lost to Follow-up**

If a site is unable to contact a subject or if the subject fails to appear for a visit, three documented phone calls should be made, followed by a certified letter (or its equivalent). The certified letter should detail the need for the subject to appear for a visit, the site's

unsuccessful attempts to contact the subject, and that failure to contact the site will result in the subject being withdrawn from the study.

If the certified letter is returned to the site as undeliverable or the letter is delivered but the subject does not contact the site and no other contact is made with the subject or the subject's caregiver, then the subject will be considered Lost to Follow-up and discontinued from the study. All attempts to contact the subject will be documented.

## **4.20 Risk and Benefits Overview**

### **4.20.1 Potential Adverse Events**

Risks to the subject may include but are not limited to the following:  
 The TPBM-1000 emits light with a longer wavelength than the human eye can see. The TPBM-1000 output is less than the maximum permissible exposure (MPE). The staff will be provided training on basic safety procedures relative to the use of the device. The staff administering the TLT will be careful not to operate the TPBM-1000 device unless it is in direct contact with the subject's skin. Both the subject receiving the TLT and the study clinician present in the TLT delivery room will wear protective eyewear in the form of goggles or eye pads. The goggles provided with the TPBM-1000 are in direct contact with the area surrounding the subject's eye. Since they are reusable they should not be shared between subjects. The eye pads are disposable and should be discarded after use. The eye pads use an adhesive to adhere to the subject's eyelids so there is potential for an allergic reaction.

Failure of the TPBM-1000, resulting in the cessation of investigative therapy can cause:

1. No adverse event to our knowledge
2. Unforeseeable adverse events

Delivery of the infrared energy to an inappropriate site, such as directly over the open eye, is not recommended and could pose a risk to the subject.

Application of the TPBM-1000 may result in mild thermal sensation of warmth during the use. The temperature of the skin is well below the level for thermal damage.

Based on human clinical trial experience to date, each adverse event listed below has been reported with TLT:

1. Application Site Erythema
2. Application Site Pain
3. Application Site Discomfort
4. Application Site Warmth
5. Application Site Reaction
6. Headache

Additional potential side effects of TLT, documented at MGH in prior trials, include:

- Seeing vivid colors, having abnormal taste
- Feeling “out-of-body” experiences
- Insomnia, restless sleep, erratic sleep, early morning awakenings
- Vivid dreams
- Irritability
- Word finding difficulties
- Abdominal bloating

Other potential risks are described below:

Risk of Worsening of Depression, Suicidality & Manic Switch: Worsening of depression and increased suicidality are possible complications of antidepressant treatments prescribed to subjects with MDD. We will minimize this risk by selecting only subjects who do not present active suicidal ideation at screening. We will also discontinue any subject who develops active suicidal ideation during the course of the study (C-SSRS) and is deemed at imminent danger; we will then arrange for appropriate levels of care and standard antidepressant treatment (see 4.8.4 Termination). Manic switches are possible adverse events and will be closely monitored during antidepressant treatment as well. Our tight schedule of clinical study visits will allow early recognition of treatment-emergent suicidal ideation or prodromal hypomanic signs. Subjects who develop mania or hypomania will be discontinued and provided appropriate level of care.

Answering detailed questionnaires may create a mild degree of inconvenience for the subjects.

Length of testing for cognitive circuitry:

The total length of this task takes a total of 40 minutes at baseline and 40 minutes at week 3, 6, 9 and 12. There is no expected risk to the patients beyond the 40 minutes of sitting in front of computer for testing and possible experience of startle. Every effort will be made to ensure that the patients are comfortable and safe during this period, and the study can be stopped at any time. Beyond these issues, there is minimal or no risk to the patients.

Risk of Bruising

Venipuncture might result in accidental bruising at the sight of blood drawing on the forearms.

**4.20.2 Benefits**

Study subjects will receive systematic MINI assessment of their DSM comorbidity. This information will be readily available to their treating clinicians if the subjects so desire and agree to disclosure. This information might guide long term treatment. In the short-term, the subject will receive close and systematic monitoring for depression and formalized cognitive assessments, beyond current standards of care. Easy access to

routine physical exams are also a potential benefit. The subjects will have access to a different modality of treatment if counseling and/ or medications were not sufficient or not acceptable to them. The treatment itself with Transcranial continuous or pulse Light Therapy (TLT) may potentially provide relief of depressive symptoms at a level equal to antidepressant medication.

## 5 Data Analysis Methods

### 5.1 General Considerations

The purpose of this study is to assess the antidepressant effect of TLT in major depressive disorder.

This feasibility study is expected to randomized 50 subjects total across two sites, 1/3-of whom will receive 12 weeks of TLT and 2/3 of whom will receive 6 weeks of sham followed by either more sham (50%) or TLT (50%) for 6 more weeks.

### 5.2 Specific Aims

A. To assess the antidepressant effect of the Transcranial continuous or pulse Light Therapy in depressed subjects.

Hypothesis 1: We anticipate that TLT will decrease QIDS-C and HAM-D 17 total scores in study subjects significantly more than the Sham treatment. We expect that we will be also able to estimate the effect size of the antidepressant action of Transcranial continuous and pulse Light Therapy, separately.

B. To assess the safety and tolerability of the Transcranial continuous / pulse Therapy in depressed subjects

Hypothesis 2: We predict that the Transcranial continuous and pulse Light Therapy will be safe and well-tolerated by depressed patients, as assessed by the following rating scales: SAFTEE-SI and ADVERSE EVENTS FORM. We anticipate differences in between TLT and Sham treatment as concerns side-effects.

Secondary Aims include the assessment of neuro-inflammation and cognitive circuitry. We predict that TLT decreases plasma levels of IL6, IL8, TNF- $\alpha$ , IL-1 $\beta$  more than sham. TLT will also improve attention, inhibition and executive functions more than sham.

### 5.3 Sample Size

With respect to the TLT study, we expect 100 subjects to sign informed consent, including screen failures. Assuming that 1/2 will screen fail this will lead to randomization of 50 subjects. In PART-1 (CW), we will have a n=24 with a 1st randomization 2:1 (sham:NIR), which will result in 16 subjects receiving sham and 8 subjects receiving NIR. We then assume 70% non-response to sham which leads to 11 sham subjects who are non-responders and who will undergo the 2nd randomization (week 6). Assuming a dropout rate of 24% before week 6, we anticipate that 9 subjects from the sham group will be eligible for the 2nd randomization 1:1 (sham:NIR). This 2nd randomization (week 6) will result in approximately 5 subjects receiving sham and 4 subjects receiving NIR. According to the Sequence Parallel Comparison (SPD) design the data from the 1st randomization (week 0 to 6 of the trial) and the data from the 2nd randomization (week 6 to 12 of the trial) can be pooled resulting in a total of 16+5=21 available sham subjects and 8+4=12 available NIR subjects. With this sample we have estimated >80% power to detect a significant difference ( $p \leq 0.05$ ) in depression outcome based

on the antidepressant effect size detected in our prior MGH study (ELATED-2). In PART-2 (PW) we will have an even larger power to detect a significant difference since our sample of subjects at the 1st randomization will be larger (n=26).

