#### **5.6 *Efficacy Analyses for Primary Aims***

The study (both PART-1 continuous and PART-2 pulse) will utilize a 2-phase sequential parallel design with 6 weeks treatment duration in each phase. Eligible patients will be randomized to two groups with a 1:2 ratio, to ensure adequate sample in phase 2 (week 6-12). Patients in the first group (TLT) will receive TLT (continuous in PART-1 and pulse in PART-2) at both phases (week 0-12). Patients in the second group (Sham) will receive sham at phase-1 and will undergo a 1:1 ratio randomization to either TLT or sham in phase-2 (week 6-12), respectively. Patient retention rates during phase-1 of the trial are assumed to be 76%, based on our earlier study ELATED-2. The treatment differences from phase-1 and phase-2 will be combined with equal weights to estimate the overall treatment effect.

For the primary efficacy analysis, all patients in phase 1 will be compared, together with sham non-responders from phase 2 (sham non-responders are defined as those patients who failed to achieve a 50% decrease in their QIDS-C score at visit 13).

A. Antidepressant effect of the TLT: To test the significance of the antidepressant effect of TLT (in both PART-1 and PART-2) we will use a T-test for mean differences of two related measures and will primarily look at QIDS-C and HAM-D 17 total score mean change on TLT and compare it with the QIDS-C and HAM-D 17 total score mean change on Sham, the significance will be set at a p-value  $\leq 0.05$ . The time-points to estimate the mean differences are baseline and week 6 for all subjects and for subjects non-responders to sham who are re-randomized also week 6 and week 12. Rates of responders according to the CGI-Improvement (score 1 or 2) will be estimated at week 6 and 12 of the study (no statistics planned). Both completer analysis and intent-to-treat analysis will be performed to analyze the severity of depression at endpoint. Patient attrition and dropouts

will be analyzed. Potential differences between treatment groups in dropouts will be examined with the Fisher's Exact test.

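### Section 5.3 takes the 24% pre-week-6 dropout off the phase-2 entrants only, so the 21 vs 12 behind the power claim is about 17 vs 10 in subjects with observed outcomes

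*Protocol*

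**What the plan says.** Protocol section 5.3 builds the PART-1 sample in steps. Twenty-four subjects are randomised 2:1, "which will result in 16 subjects receiving sham and 8 subjects receiving NIR". Non-response is then applied: "We then assume 70% non-response to sham which leads to 11 sham subjects who are non-responders". Dropout comes next: "Assuming a dropout rate of 24% before week 6, we anticipate that 9 subjects from the sham group will be eligible". The second randomisation "will result in approximately 5 subjects receiving sham and 4 subjects receiving NIR". Finally the phases "can be pooled resulting in a total of 16+5=21 available sham subjects and 8+4=12 available NIR subjects", and the section concludes: "With this sample we have estimated >80% power to detect a significant difference". The effect is described only as the one seen in ELATED-2. PART-2 (n=26) is said to have more power still.

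Section 5.6 repeats the attrition assumption without limiting it to sham: "Patient retention rates during phase-1 of the trial are assumed to be 76%, based on our earlier study ELATED-2". On the outcome it says: "The time-points to estimate the mean differences are baseline and week 6 for all subjects", with week 6 and week 12 added for re-randomised sham non-responders. The test is a t-test on mean change, and the two phase differences receive equal weight. No dropout rate is given for weeks 6-12.

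**The concern.** One attrition assumption is used in two ways. Sham subjects lost before week 6 are removed when counting who reaches the second randomisation, but the same subjects, and the NIR subjects lost at the same rate, stay in the count for a comparison whose outcome is measured at week 6. The 9 re-randomised subjects are then carried to week 12 without loss. If the counts are meant as subjects with an observed outcome, the power statement rests on more data than the plan expects to have. If they are meant as all randomised subjects, the effect size must come from the same kind of set, and the reader cannot tell whether it did. The PART-2 statement uses the same method and inherits the ambiguity.

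**Working it through.** **Inputs.** From 5.3: 24 randomised, 2:1 sham:NIR, 70% sham non-response, 24% dropout. From 5.6: 76% phase-1 retention, equal phase weights, significance at 0.05. Two-sided testing is assumed; the power formula quoted in the SAP uses 1.96, which agrees. From 3.1, the ELATED-2 HAM-D-17 changes:

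- Endpoint sample: 11.7 (SD 7.5, n=9) vs 5.3 (SD 7.0, n=9). Difference 6.4; pooled SD √[(7.5² + 7.0²)/2] = 7.25; d = 0.88.
- Completers: 15.7 (SD 4.4, n=6) vs 6.1 (SD 7.9, n=7). Difference 9.6; pooled SD √[(5×4.4² + 6×7.9²)/11] = 6.55; d = 1.47.

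**Plan's counts reproduced.** 24 × 2/3 = 16 sham, leaving 8 NIR. 16 × 0.70 = 11.2; 11.2 × 0.76 = 8.5, about 9, split 5 and 4. 16 + 5 = 21 and 8 + 4 = 12.

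**Counts with the plan's retention in both phase-1 arms.** 16 × 0.76 = 12.2, about 12 sham; 8 × 0.76 = 6.1, about 6 NIR. The 5 and 4 already reflect the loss. Pooled: 12 + 5 = 17 sham and 6 + 4 = 10 NIR.

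**Sensitivity only.** If 24% were also lost in phase 2 (an assumption; the plan gives no rate), 9 × 0.76 = 6.8, about 4 sham and 3 NIR, giving 16 vs 9.

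**Power formulas.** Equal phase weights: standardised SE = √[0.25(1/n₁ₐ + 1/n₁ₛ) + 0.25(1/n₂ₐ + 1/n₂ₛ)], where a is NIR and s is sham, noncentral t with df = total phase-observations − 4. Pooled t-test: SE = √(1/nₐ + 1/nₛ), df = nₐ + nₛ − 2. Noncentrality is d/SE.

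| Counts, NIR/sham (phase 1; phase 2) | SE weighted | d = 0.88: weighted (pooled) | d = 1.47: weighted (pooled) |
|---|---|---|---|
| 8/16; 4/5 (as printed) | 0.399 | 57% (66%) | 94% (98%) |
| 6/12; 4/5 (76% in phase 1) | 0.418 | 52% (57%) | 92% (94%) |
| 6/12; 3/4 (24% phase-2 loss also assumed) | 0.456 | 45% (53%) | 87% (92%) |

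Only two kinds of cell pair like with like: printed counts with the endpoint effect (57% weighted, 66% pooled), and retained counts with the completer effect (92% weighted, 94% pooled; 87% and 92% with the assumed phase-2 loss). A one-sided pooled test at 21 vs 12 with the endpoint effect gives 77%, still below 80%.

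**PART-2.** 26 × 2/3 = 17.3, so about 17 sham and 9 NIR. 17 × 0.70 × 0.76 = 9.0, split 5 and 4. The plan's method then gives 22 vs 13, and the pooled test has 69% at the endpoint effect.

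**The case against.** A reader might infer that 21 vs 12 is impossible. It is not. A subject must be present at week 6 to be re-randomised, but need not be to count in phase 1. Section 4.5 treats a subject as analyzable after one session, section 5.6 compares all phase-1 patients and plans an intent-to-treat analysis beside the completer one, and the SAP uses a constrained longitudinal model. QIDS-C is scheduled at visits 3, 5, 7, 9, 11 and 13, so many early leavers would have post-baseline scores. The same reasoning can keep re-randomised subjects who leave later in phase 2. This stands: 21 vs 12 can be an all-randomised count. But 5.3 does not say so, and 5.6 describes a t-test on change to week 6 with no rule for a missing week-6 score.

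A reader might also quote 52% or 45% as the corrected power. Those cells apply the endpoint effect, which is reported separately from the completers and so already reflects non-completers, to counts from which non-completers have been removed. That penalises dropout twice. Nor is the printed-count t-test power a proven ceiling for the longitudinal analysis, because such a model can gain precision from baseline and earlier scores.

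The 9 entrants are not a slip either. Starting from the rounded 11 gives 8.4, but the unrounded chain gives 8.5. Finally, section 5.1 calls this a feasibility study, which limits how much rests on an exact power figure.

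**Conclusion.** The concern holds as an inconsistency between the counts in 5.3 and the plan's own retention and outcome definition. With observed outcomes, PART-1 yields about 17 vs 10 (27 phase-observations rather than 33), and fewer with any phase-2 loss.

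The documents do not support the further step that correcting dropout brings power below 80%. At the completer effect, power stays above 80% in every scenario shown; at the endpoint effect it is below 80% already at the printed counts. What fails is the pairing. Of the two ELATED-2 effects reported, only the completer effect gives more than 80%, and its matching counts are the retained ones. The printed counts match the endpoint effect, which gives 57% weighted or 66% pooled.

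These figures assume two-sided 0.05, the same true effect in both phases, a HAM-D-17 effect size carried over to QIDS-C, and independence between phases. The 16 vs 9 and 87% figures also rest on a phase-2 dropout rate that the plan does not give.

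**What to change.** In section 5.3, choose one basis and state it:

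- **Observed outcomes:** apply 76% retention to both phase-1 arms (12 + 5 = 17 sham, 6 + 4 = 10 NIR) and use the completer effect; or
- **All randomised subjects:** keep 21 vs 12, say that dropouts contribute their available QIDS-C scores through the SAP's longitudinal model, use the endpoint effect, and give power for that analysis.

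Either way, name the ELATED-2 effect used, state how a missing week-6 or week-12 score is handled, show phase-2 loss as a sensitivity range, and restate power for PART-1 and PART-2. The cost is one recalculation and a few sentences. No extra patients are needed, though the stated power may become less favourable.

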### 3.1 Summary of Prior Clinical Experience

We conducted two studies on the safety and efficacy of TLT delivered to the forehead (prefrontal cortex) twice a week in subjects with MDD.

ELATED-1 was a proof of concept study of 3 weeks of TLT (Neurothera - class IV laser, wavelength 808 nm; irradiance 700 mW/cm^2; fluence of 84 J/cm^2; total energy 2.4 kJ per session for 6 sessions) ([name] et. al. 2015). All subjects (n=4) were treated with TLT. Baseline mean HAMD-17 scores for depression decreased from 19.8±4.4 (SD) to 13±5.35 (SD) after treatment (p=0.004).

ELATED-2 was a double-blind, randomized, controlled study of 8 weeks of TLT (Omnilux New U - LED, 830 nm; 36.2 mW/cm^2; up to 65.2 J/cm^2; vs. sham for 16 sessions). At endpoint, the mean HAMD-17 for depression decreased of 11.7±7.5 points (TLT, n=9) vs. 5.3±7.0 points (sham, n=9) (p=0.04); the differences were even more pronounced in the completers sample as HAMD-17 decreased of 15.7±4.4 (TLT, n=6) points vs. 6.1±7.9 points (sham, n=7) (p=0.01).

These findings suggest that TLT could be a novel intervention for patients with MDD. Both the Laser study (ELATED-1) and the LED study (ELATED-2) were conducted by our group at MGH. ELATED-3 (the present submission) will test for the first time pulse light therapy (p-TLT) in a comparable population of MDD subjects.

The LiteCure® PhotoBioModulation-1000 (TPBM-1000) device to be used in this study does not require FDA approval. In fact, the TPBM-1000 device used in this study is considered a non-significant risk device because:

- TPBM -1000 dose does not exceed the Maximum Permissible Exposure (MPE) for skin – Center for Devices and Radiological Health (CDRH), 21CFR1040.10 and 21CFR1040.11;
- TPBM-1000 is substantially equivalent to the OmniLux New U device (used in ELATED-2 at MGH), which the FDA has already categorized as a non-significant risk device;
- TPBM-1000 differs from the OmniLux New U only in that it provides an additional site of irradiation – treatment is delivered to EEG sites FP1 and FP2 in addition to F3 and F4 on the forehead;
- currently FDA-cleared LED devices are typically available over-the-counter and are considered safe to use without professional supervision.

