### ***4.5 Sample Size***

The ELATED-3 Study is expected to include 50 subjects with analyzable data (at least 1 session post randomization).

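### The >80% power stated for PART-1 in section 5.3 does not hold at the ELATED-2 effect that fits the primary comparison; two-sided power there is about 57–60%

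*Protocol*

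**What the plan says.** Protocol section 5.3 builds the PART-1 sample in steps. Of 24 randomised subjects, 16 go to sham and 8 to active light. With 70% sham non-response, 11 sham subjects go forward. Then: "Assuming a dropout rate of 24% before week 6, we anticipate that 9 subjects from the sham group will be eligible" for the second randomisation, split 5 and 4. The two phases are added together, "resulting in a total of 16+5=21 available sham subjects and 8+4=12 available NIR subjects". The conclusion is "With this sample we have estimated >80% power to detect a significant difference" at p ≤ 0.05, based on the ELATED-2 effect. For PART-2, with 26 subjects, the section says only that "we will have an even larger power to detect a significant difference".

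Section 3.1 gives two ELATED-2 results. At endpoint, "the mean HAMD-17 for depression decreased of 11.7±7.5 points (TLT, n=9) vs. 5.3±7.0 points (sham, n=9) (p=0.04". In completers, "HAMD-17 decreased of 15.7±4.4 (TLT, n=6) points vs. 6.1±7.9 points (sham, n=7) (p=0.01".

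Section 4.5 expects "50 subjects with analyzable data (at least 1 session post randomization". Section 5.6 defines the primary comparison as all phase 1 patients plus the phase 2 sham non-responders, tests mean changes with a t-test, and combines the two phase differences with equal weights. It also plans both a completer and an intent-to-treat analysis. The SAP's Primary Analysis section names a constrained longitudinal model.

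**The concern.** Section 5.3 gives no effect, SD, sidedness, test or phase weights, and the choice between the two ELATED-2 effects decides whether the claim is true. The plan's own analysis set points to the smaller effect: section 5.6 compares everyone in phase 1, section 4.5 counts anyone with one session as analysable, and section 5.3 takes no dropout off the 16 + 8. Applying a completer effect to a count that includes dropouts would mix two populations. Sections 5.3 and 5.6 also differ on the estimator, since one pools the observations and the other weights the phases equally.

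This sentence is the only power justification for the sample size. If PART-1 gives a null result, a reader who trusts the figure will think the chance of missing the ELATED-2 effect was under 20%. At the endpoint effect it is about 40–43% with equal weights, or 32–34% pooled.

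**Working it through.** **Inputs.** The ELATED-2 means, SDs and group sizes are from section 3.1; the counts 16/8 and 5/4 from section 5.3; the equal weights and 76% retention from section 5.6. Sidedness is not stated in 5.3 or 5.6. Two-sided 0.05 is assumed here because the formula quoted in the SAP uses 1.96. Other assumptions: unadjusted change scores, the same effect and SD in both phases, and independent phase estimates. Each range runs from the noncentral t to the normal approximation, unless a method is named.

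**Effect sizes.**
- Endpoint: pooled SD = √((7.5² + 7.0²)/2) = 7.254; d = 6.4/7.254 = 0.882. The 95% CI for d from 9 vs 9 is −0.10 to 1.84.
- Completers: pooled SD = √((5×4.4² + 6×7.9²)/11) = 6.545; d = 9.6/6.545 = 1.467.

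**Can the stated figure be reproduced?** Yes, at the completer effect. Power follows from d/√V, where V is the variance of the estimator in SD² units.
- Pooled, 21 vs 12: V = 1/21 + 1/12 = 0.1310, 31 df. Power 97.5–98.2%.
- Equal weights: V = 0.25 × (1/16 + 1/8 + 1/5 + 1/4) = 0.1594, 29 df. Power 94.4–95.7%.
- Equal weights with phase 1 cut to 12/6 (16×0.76 = 12.2; 8×0.76 = 6.1): V = 0.175, 23 df. Power 91.9–93.9%.

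**The same sample at the endpoint effect, d = 0.882.**

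| Estimator | Two-sided | One-sided |
|---|---|---|
| Equal weights, 16/8 and 5/4 | 57.0–59.9% | 69.6–71.4% |
| Pooled, 21 vs 12 | 65.6–68.4% | 77.0–78.6% |
| Equal weights, 12/6 and 5/4 | 52.4–55.9% | 65.6–67.9% |

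Other phase 1 weights do not rescue the figure. The best is about 0.7, and it gives 65–68% two-sided. If d is scaled by the sham SD instead (6.4/7.0 = 0.914), one-sided power is 79.6–81.1% pooled and 72–74% with equal weights. Among these unadjusted versions, only the pooled, one-sided, normal-formula one with the sham SD passes 80%.

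**Detectable d at 80%, two-sided.** Pooled: 1.01 (normal) to 1.05 (t). Equal weights: 1.12 (normal) to 1.16 (t).

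**A larger phase 2 effect.** With equal weights and a phase 1 d of 0.882, a 25% larger phase 2 effect (d = 1.103) gives 67–70%. Reaching 80% needs a phase 2 d of 2×1.118 − 0.882 = 1.35 (normal) to 2×1.157 − 0.882 = 1.43 (t). Multiplied by 7.254, that is about 9.8–10.4 points, and no document gives such a figure.

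**PART-2.** A 2:1 split of 26 is 17/9. Applying the 5.3 rates, 17×0.70×0.76 ≈ 9 enter phase 2. With 5/4 to 5/5 assumed there, two-sided power at d = 0.882 is 58–65% with equal weights and 69–73% pooled.

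**The ELATED-2 p-values.** From the printed summaries, the endpoint t is 1.87 on 16 df: p = 0.080 two-sided, 0.040 one-sided. The completer t is 2.64 on 11 df: p = 0.023 two-sided, 0.012 one-sided. The printed 0.04 and 0.01 match the one-sided values.

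**The case against.** The claim is a lower bound, and one of the two ELATED-2 effects satisfies it easily. Section 5.3 does not say that it used the endpoint effect, and section 5.6 plans a completer analysis. On that reading the fault is an unnamed assumption rather than a miscalculation. This stands in part: the figure is reproducible, but only with an effect that does not match the all-patient primary comparison.

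The strongest point is that 57–60% is not the power of the SAP's longitudinal model. With equal variances over time, baseline adjustment multiplies the change-score variance by (1 + ρ)/2. No document gives ρ. For assumed values of 0.3, 0.5 and 0.7, two-sided power at the endpoint effect is:
- equal weights: 75–78%, 69–72% and 64–67%;
- pooled: 83–86%, 78–80% and 73–75%.

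An assumed 20% smaller SD in phase 2 gives 70–73% with equal weights and unadjusted scores, and 81–84% when combined with ρ = 0.5. One-sided testing with ρ = 0.5 gives 80–82% with equal weights. So 80% can be reached at the endpoint effect, but only by adding pooling, one-sided testing or a smaller phase 2 SD to a favourable correlation, and none of those values is in the documents.

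It is also fair that the 1.96 comes from an appendix written for response rates, and that the ELATED-2 p-values suggest one-sided testing there. One-sided power is therefore shown above; at the endpoint effect with equal weights and unadjusted scores it is still 70–71%.

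Finally, section 5.1 says: "This feasibility study is expected to randomized 50 subjects total across two sites". Low power is acceptable in a feasibility study if it is stated as such.

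**Conclusion.** The concern holds. For the analysis described in section 5.6 (all phase 1 patients, t-tests on mean change, equal phase weights), the stated >80% is not delivered at the ELATED-2 endpoint effect. Two-sided power is about 57–60%, or 66–68% with the pooling of section 5.3. The claim is true only if the completer effect is meant, or if further favourable assumptions are made that the plan does not state.

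These figures rest on two-sided testing, unadjusted change scores, and equal effects and SDs in both phases. They also carry an HAM-D-17 effect over 8 weeks across to QIDS-C over 6-week phases. The CI for the endpoint d (−0.10 to 1.84) shows that no single power figure here should be read as precise. The point should be fixed; it does not put the design in doubt.

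**What to change.** In section 5.3:
- Name the ELATED-2 effect, SD, sidedness, test and phase weights, and note the differences in scale and duration between the two studies.
- Replace >80% with the power of the primary estimator at the endpoint effect: about 57–60% with equal weights, 66–68% if pooled. Show the completer-effect figures (94–96% and 97–98%) beside it as the optimistic case.
- Add the detectable d at 80% power (1.12–1.16 with equal weights, about 1.05 pooled) and the CI of the endpoint d.
- State that the same effect is assumed in both phases, or give the phase 2 effect that was assumed.
- Give PART-2 a number with its split: about 58–65% with equal weights and 69–73% pooled, for 5/4 to 5/5 in phase 2.
- If the SAP's longitudinal model is primary, recompute for that model and state the correlations, variances and phase weight used.

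In section 3.1, state which test gave the ELATED-2 p-values.

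The cost is a change of wording and numbers, plus one recomputation if the SAP model is primary. Enrolment does not change. The stated power becomes less favourable unless the completer effect is named and justified.
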